### **13.0 SELECTION CRITERIA FOR INVESTIGATORS/SITES**

- The Investigator/s selected to participate in this study is/are qualified Orthopaedic surgeon/s.
- Research assistants and study staff will be representatives of the Institute under the direction of the Principal Investigator.
- Any conflicts of interest (including financial assistance from other parties) will be declared by investigators and research personnel before the commencement of the trial.
- Investigators must maintain a list of any delegated duties with respect to the trial, and the persons and qualifications of those persons to whom the duties are assigned.
- Sites must be able to demonstrate that adequate subject recruitment is likely to be possible, with necessary time available to conduct the study to GCP requirements, and with adequate facilities and trial staff.
- Investigators must provide medical care to a trial participant that is necessary as a result of any adverse event experienced during or following the trial that is deemed related to the trial.
- Investigators must possess, prior to trial commencement, a favorable Human Research Ethics Committee (HREC) endorsement of trial protocol, patient information and consent forms and any other information given to subjects.
- All trial related documents are subject to HREC review. A regular trial report is also mandatory for provision to the HREC (in accordance with local HREC requirements).
- The investigator/institution shall permit trial related monitoring, audits, HREC review and regulatory inspections, by providing direct access to source data/documents and any other trial related documentation.
- The trial MUST be conducted according to the approved protocol.
- Any deviation from the protocol must be documented for later review.

- No deviation from protocol may occur without HREC endorsement, unless it is required to prevent imminent harm to participants
- Investigators must ensure subjects have given informed, written consent, with all trial procedures and risks adequately explained.

## **14.0 ADMITTANCE OF PATIENT**

The Investigator must wait for written Ethics Committee and Governance approval prior to beginning the study or enrolling participants.

A review of the inclusion and exclusion criteria must be completed by the Investigator pre-operatively for each patient.

A patient will be identified as a patient in this clinical trial upon signing a study informed patient consent form.

## **15.0 PATIENT ACCOUNTING**

The investigator or designee will complete an informed consent log with details (patient number and initials) of any patient signing a consent form to participate in this study.

Clinical trial data will be monitored regularly to identify any trends and adverse events. Documentation of participants who voluntarily withdraw from the study or who are lost to follow-up will be obtained on a Study Completion Form.

## **16.0 QUALITY ASSURANCE OF DATA**

Case Report Forms will be routinely reviewed by the Principal Investigator for completeness and accuracy as well as any evidence which may be indicative of patient risk. When any discrepancies are noted, they will be resolved with the Investigator and/or individual designated by the Investigator. When the data are incomplete, attempts will be made to obtain the data whenever possible.

Stryker Australia will monitor each investigational site at regular intervals to ensure compliance with the protocol and capture of any data or complications not already

documented. Verification of the data from source documents will also be conducted by the Stryker monitors.

## **17.0 MANAGEMENT OF CONCURRENT EVENTS**

### **17.1 Concurrent illness/procedures**

Participants requiring concurrent procedures or medications for inter-current illnesses or adverse events will not be restricted throughout the study. Given the typical patient population receiving total knee joint replacements, it can reasonably be expected that concurrent illnesses or procedures may be experienced by study participants.

### **17.2 Withdrawal from Study**

Participants will be advised that they may voluntarily withdraw from the study at anytime, for any reason and they are not obligated to reveal the reason to the Investigator and it will not affect their medical care. However, in such cases, appropriate effort will be made to determine the reason for withdrawal from the study. The Investigator may request a letter from the patient noting his or her desire to withdraw from the study. All attempts to locate participants lost to follow up will also be documented.

Participants will be informed that should they withdraw from the study they should remain under the care of an appropriately experienced physician until the physician deems further follow-up unnecessary.

The following are circumstances for which a patient would be identified as not continuing their participation in the study:

- Study Completed / Terminated
- Death
- Unable to Return
- Unwilling to Return
- Concurrent Illness
- Lost to follow-up

- Re-operation of the affected knee joint, including revision of total knee replacement components
- Other

Additionally, the patient may be withdrawn by the Investigator, if he/she is unable to continue participation in the study due to some condition unrelated to this study.

A Study Completion Form will be completed for all participants who withdraw from the study.

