### **3.0 OBJECTIVES**

The primary endpoints of this study are:

1. Repeatability of cutting guide position on the distal femur and proximal tibia assessed by repeated measures using computer navigation system for total knee replacement, assessed intra-operatively (Group A).
2. Radiographic implant location, consisting of multi-parameter assessment of the relative position and orientation of the femoral and tibial components and overall limb alignment, assessed by the Perth CT protocol 3 months after surgery (Group B).

The secondary endpoint of this study is:

3. Knee function, quality of life and pain assessed 6 months after surgery (Group B).

The study objectives are:

1. Repeatability of the cutting guide position will be no worse than that obtained for manual instruments used for total knee replacement (Group A).

2. Participants will have higher knee function scores and increased quality of life as compared to pre-operative state and equal or better as compared to other surgical techniques using historical controls (Group B)

The objectives of the Extension Study are:

1. The primary objective is to determine the clinical and radiographic outcomes at 12 months, 2 years and 5 years post surgery, in patients receiving a Triathlon Custom Fit Knee featuring Stryker ShapeMatch.
2. The secondary objective is to determine the revision rate (yearly cumulative percent revision), device-related adverse events and reoperation rates.

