**VAS:** A Visual Analogue Scale (VAS) is a measurement instrument that tries to measure a characteristic or attitude that is believed to range across a continuum of values and cannot easily be directly measured. For example, the amount of pain that a patient feels ranges across a continuum from none to an extreme amount of pain. From the patient's perspective this spectrum appears continuous - their pain does not take discrete jumps, as a categorization of none, mild, moderate and severe (Wewers et al, 1990).

**FJS-12:** The Forgotten Joint Score is a newly-developed twelve-item, self-reported assessment of how aware recipients of hip and knee joint replacement are of their joint in everyday life (Behrend et al, 2012).

**Medical History Review:** For participants in the extension study, details of any significant medical events from time of surgery to 12 month visit will be recorded to ensure no adverse events have occurred between termination from Group B study and re-enrolment into Extension study.

All information on general medical, operative and device related complications will be documented and tabulated on case report forms (CRF).

All information on complications (date of occurrence, description, severity, related to study device, treatment and resolution) will be recorded at the time of occurrence.

All information on protocol deviations including the type of deviation (informed consent, inclusion/exclusion criteria, treatment, tests not performed and follow-up) will be recorded at the time of occurrence.

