## **12.2 Data Capture and Analysis**

All data will be recorded on 2-part NCR paper Case Report Forms (CRFs). The surgeon will complete and sign forms at the time of completion. Original CRFs will be collected by Stryker for data entry. Copies will remain at the investigator site. Archiving will be undertaken in accordance with ICH/GCP guidelines (Appendix 6).

Any unclear or ambiguous data will be queried and all cleaned data will be entered into a database for tracing purposes.

The primary outcome data gathered from Group A will be assessed using a repeated-measures analysis (Hopkins, 2009) to determine the mean and standard error of measurement between successive pairs of trials. Multiple surgeons gathering repeated measures on individual patients will be pooled to take into account varying knee anatomies and intra-observer variation.

The data from Group B and the Extension Study will be summarised and descriptive statistics will be utilised for analysis of the primary and secondary outcomes. The mean, median, standard deviation, minimum and maximum will be presented for quantitative variables. Statistical tests will be employed as deemed appropriate by a biostatistician. A significance level of 0.05 will be used for comparative tests.

Adverse events will be tabulated separately and reviewed for any commonalities.

Revision surgery data from the Extension Study will be compared to the revision rates reported in the National Joint Registry Report at 12 months, 2 years and 5 years. A cost benefit analysis will be undertaken with the use of data from the Australian Government Hospital Casemix Protocol Annual Report.

A formal interim analysis will take place following completion of each Group A and Group B sub-studies. Additionally, formal interim analyses will take place following all

participants' completion of the 12 month visit, again following completion of all participants' 2 year visit and final analysis will take place following completion of all participants' 5 year follow-up visits.

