## **19.2 Reporting of Events**

### **Adverse Events:**

***Any adverse event that occurs at any time point from the beginning of the surgical procedure until either the patient is terminated from the study, or 30 days post-completion, should be recorded as follows:***

All information on general medical, operative and device related complications (adverse events) will be documented on case report forms (CRFs). Information should include date of occurrence, description, severity, relationship to study device, treatment and date of resolution.

The investigator must determine if the event is related to the device. Any adverse event in a study patient must be monitored until the event is resolved or considered non-clinically significant by the Investigator.

**Expected Events:** Should be reported to the sponsor soon as possible, but not later than ten working days after the Investigator first learns of the effect.

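### Read as a rule, Section 17.2 ends participation at any re-operation of the study knee, even with the implant retained, so later revisions, repeat re-operations and scores may not reach the 5-year Extension data

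*Combined protocol and SAP*

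**What the plan says.** Section 17.2 opens its list with "The following are circumstances for which a patient would be identified as not continuing their participation in the study". One entry is "Re-operation of the affected knee joint, including revision of total knee replacement components". Revision is only one included case, so a re-operation that leaves the components in place is covered too. Nothing exempts the Extension, which has no withdrawal rule of its own. Sections 6.3 and 6.4 govern entry only, and the sole knee-related bar in 6.4 is an implant that has been revised or is no longer in place.

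Section 3.0 makes clinical and radiographic results at one, two and five years the Extension's primary objective. The secondary objective is to "determine the revision rate (yearly cumulative percent revision), device-related adverse events and reoperation rates". Under Section 12.2, revision data will be "compared to the revision rates reported in the National Joint Registry Report at 12 months, 2 years and 5 years".

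Section 19.2 records adverse events "until either the patient is terminated from the study, or 30 days post-completion", with the same end for serious events. It also requires an open event to be followed until it resolves or the investigator judges it no longer clinically significant.

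Section 17.1 points towards continued participation: "Participants requiring concurrent procedures or medications for inter-current illnesses or adverse events will not be restricted throughout the study".

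**The concern.** A study that sets out to report revision and re-operation over five years appears to stop observing a knee once it has shown a problem. An implant-retaining re-operation is acceptable at Extension entry under 6.4, but under 17.2 it ends participation if it happens afterwards.

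If such knees are later revised more often than the rest, ending their follow-up is informative censoring. The revision rate set beside the registry figures would then be too low, and enrolling more patients would not remove the error. Repeat re-operations would be undercounted, and late scores would be averaged over knees that had done better.

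**Working it through.** **Step 1: what is captured and what is not, if 17.2 is a rule.**

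- Captured: the triggering re-operation, a first revision, and the share of patients with at least one re-operation, through the adverse event forms and the Study Completion Form.
- Possibly captured: a later revision for the same unresolved problem, through the follow-up of open events in 19.2. Site monitoring under Section 16.0 may also pick up undocumented complications.
- No planned route: other later revisions, repeat re-operations, new adverse events after termination, and later scores. Section 12.2 compares with published registry rates; it does not describe linking study patients to the registry.

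**Step 2: the same question, if the list is only a menu of exit reasons.** A patient who has not exited stays on the Extension schedule in Section 1.0, with adverse events collected at 12 months, 2 years and 5 years. Loss then occurs only where a site records re-operation as the reason for exit.

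**Step 3: size.** The plan gives no revision or re-operation rate, so there is no figure of its own to reproduce here. (Its 87 per group in 12.1 does reproduce: a two-sided t-test with difference 15 and SD 35 gives 86.4, rounded up. It does not bear on revision.) All of the following are assumptions:

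- p, the share with an implant-retained re-operation: 2-5%
- q, the probability of revision within 5 years of it: from 4% (same as other knees) to 20%
- R, the true 5-year revision rate: 4%

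For early re-operations, R = pq + (1 - p)r, where r is the revision rate in the other knees. An estimate censored at re-operation therefore reads r = (R - pq)/(1 - p), and the missed revisions per 100 knees are 100pq.

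For re-operations spread evenly over 5 years, with constant hazard h = -ln(1 - q)/5, the effective q is 1 - (1 - exp(-5h))/(5h). This is 0.051 for q = 10% and 0.104 for q = 20%. The evenly spread estimates below come from a simulated Kaplan-Meier curve.

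| p | q | Timing | Missed per 100 | Censored estimate |
|---|---|---|---|---|
| 5% | 4% | early | 0.2 | (0.04 - 0.002)/0.95 = 4.0% |
| 2% | 10% | even | 2 x 0.051 = 0.10 | 3.9% |
| 2% | 10% | early | 0.2 | (0.04 - 0.002)/0.98 = 3.88% |
| 5% | 20% | even | 5 x 0.104 = 0.52 | 3.6% |
| 5% | 20% | early | 1.0 | (0.04 - 0.01)/0.95 = 3.16% |

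If follow-up of open events catches half of the later revisions, the missed counts halve. The first row still misses 0.2 revisions per 100 in a crude count, but the censored estimate is unbiased.

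A cross-check in hazard terms agrees. With 3% baseline revision and 5% re-operated, a hazard multiplier of 1 gives 3.00% true and 3.00% censored. A multiplier of 5 gives 3.29% true and 3.00% censored, with 0.36 revisions missed per 100. A much harsher assumption (5% baseline, 10% re-operated, multiplier 10) gives 6.92% against 5.00%. The documents offer no basis for choosing among these.

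**Step 4: sampling error.** The exact (Clopper-Pearson) 95% interval for 4 of 100 is 1.1-9.9%.

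**Step 5: late scores.** If the lost 2-5% score an assumed 20-40 points below the others, the mean Knee Society Score shifts by 0.02 x 20 = 0.4 to 0.02 x 20 x 5 = 2.0 (that is, 0.05 x 40) of 200 points. The standard error with SD 35 and n = 100 is 35/sqrt(100) = 3.5.

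**The case against.** The strongest reply is that 17.2 only catalogues exit reasons. The list runs from study completion to a catch-all, includes patients unable or unwilling to return, and leads to the Study Completion Form. It also names concurrent illness; as an automatic trigger, that entry would clash with 17.1, whose allowance for procedures needed because of adverse events arguably covers an implant-retaining re-operation. The menu reading also fits the re-operation objective in 3.0. This stands as a fair reading, but the lead-in and the unqualified entry support the other one, and no text settles the matter.

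A reader might infer that these knees are lost on either reading because nothing says they stay in follow-up. The documents do not support that: a participant who has not exited remains on the visit schedule by default.

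A reader might also infer that the revision rate is bound to be understated. That needs re-operated knees to be revised more often than others, which the documents neither state nor quantify.

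The safeguards are real but partial. For Extension entrants, the history review in Section 11.0 covers surgery to 12 months and is meant "to ensure no adverse events have occurred between termination from Group B study and re-enrolment into Extension study". It picks up early re-operations but not events after an exit in, say, year 2. The new information sheet for the Extension and the case report forms were not available for this check and may say more.

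**Conclusion.** The point holds as an ambiguity with a modest consequence, and its severity is low. Under the rule reading, implant-retained re-operation cuts off data that the Extension's own objectives call for. Under the menu reading, the loss depends on how each site uses the list.

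With 2-5% re-operated, later revision between 4% and 20%, and a true rate of 4%, the censored 5-year estimate lies between 4.0% and 3.2%. The low end needs the highest re-operation and revision shares together, all re-operations early, and no later revision caught. The whole range is well inside sampling error, and the assumed score shift is below one standard error. Any bias in the revision rate is downward only if re-operated knees are revised more often. The Group A repeatability endpoint and the Group B CT endpoint at 3 months are essentially unaffected.

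**What to change.** Amend 17.2 so that re-operation without component revision does not end data collection for consenting patients: revisions, re-operations, adverse events and scores continue at the visits already scheduled. Reconcile 17.2 with 17.1 and 6.4, and say expressly whether the list is a rule or a set of exit reasons. Section 12.2 should then state how scores after a re-operation enter the summaries.

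A secondary wording point: Section 5.0 issues the Extension invitation at completion of the 6-month visit, whereas 6.3 requires only the 3-month visit and 12.1 invites all 100 cases. These should be aligned, so that it is clear how a patient who leaves Group B between those visits is approached.

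The cost is an amendment with ethics approval and already scheduled visits for about 2-5 patients per 100 under the assumed rates. Reported revision rates and late scores may look slightly less favourable.

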## **18.0 MODIFICATION OF PROTOCOL**

**No changes** to this Protocol will be permitted without the written approval of the applicable Ethics Committee.

Protocol deviation details should be recorded on a Protocol Deviation Form as soon as identified and notification will be made to the applicable Ethics Committee according to the Ethics Committee requirements.

## **19.0 DEFINITIONS AND REPORTING OF ADVERSE EVENTS**

### **19.1 Definitions**

#### **Adverse Events:**

Any undesirable clinical occurrence in a subject, whether it is considered to be device related or not, that includes a clinical sign, symptom or condition and/or an observation of an unintended technical performance or performance outcome of the device.

**Expected:** An adverse event is expected when the specificity and severity of the event is consistent with a complication that is not related to the device but may be related to the surgical procedure.

**Unexpected:** An adverse event is unexpected when the specificity or severity of an adverse event is not consistent with the standard. It refers to an adverse event that has not been observed before.

### **Adverse Device Event**

A clinical sign, symptom or condition that is causally related to the product, implantation procedure, the presence of product or the performance of the device system.

### **Serious Adverse Advent (SAE):**

Any untoward medical occurrence that:

- Results in death,
- Is life threatening,
- Requires inpatient hospitalization or prolongation of hospitalization,
- Results in persistent or significant disability/incapacity,
- Is a congenital anomaly/birth defect, or;
- Is a medically important event or reaction.

## **19.2 Reporting of Events**

### **Adverse Events:**

***Any adverse event that occurs at any time point from the beginning of the surgical procedure until either the patient is terminated from the study, or 30 days post-completion, should be recorded as follows:***

All information on general medical, operative and device related complications (adverse events) will be documented on case report forms (CRFs). Information should include date of occurrence, description, severity, relationship to study device, treatment and date of resolution.

The investigator must determine if the event is related to the device. Any adverse event in a study patient must be monitored until the event is resolved or considered non-clinically significant by the Investigator.

**Expected Events:** Should be reported to the sponsor soon as possible, but not later than ten working days after the Investigator first learns of the effect.

### **Adverse Device Events**

Should any adverse device events occur, the study staff will ensure that these are documented by the Investigator and reported immediately to the Sponsor. They should also be reported to the reviewing Ethics Committee and Institution as soon as possible, but not later than fifteen working days after the Investigator first learns of the effect, unless an earlier timeline is specified by individual study sites. The Investigator with the Sponsor will conduct an evaluation of such effects. Following this evaluation, if the Investigator determines that an unanticipated adverse device effect presents an unreasonable risk to participants, the Investigation will be terminated as soon as possible. Termination shall occur no later than five working days after the Investigator makes this determination and no later than fifteen working days after the Investigator first receives notice of the unanticipated adverse effect.

